10.3.5. Exploratory Analyses

10.3.5.1. %SPT area

For each patient the % SPT area (the area of SPT as a percentage of the total area of all TWs) will be calculated. From this a binary variable will be computed indicating whether % SPT area is $< 25\%$ or $\geq 25\%$. Cumulative and absolute frequencies for each category will be computed.

10.3.5.2. %TBSA

A binary variable indicating whether total %TBSA of all TWs is $\leq 15\%$ or $> 15\%$ will be calculated per patient. For this variable cumulative and absolute frequencies for each category will be computed.

10.3.5.3. *Application data*

For the patients of the NexoBrid and the gel vehicle arm the number of applications (0, 1, 2) will be determined. Cumulative and absolute frequencies will be computed for each category. Furthermore, for each patient the amount of NexoBrid gel each patient in the NexoBrid treatment arm has been exposed to, will be calculated.

10.3.5.4. *Maintenance of complete wound closure*

For each follow-up visit the information of complete wound closure for each TW will be aggregated to a binary variable indicating maintenance of complete wound closure on a patient level (i.e. complete wound closure for each TWs of a patient). Cumulative and absolute frequencies will be computed for each category.

10.3.5.5. *% wound area surgically excised for eschar removal*

% of wound area surgically excised for eschar removal, A_{total} , will be calculated using the following formula:

$$A_{total} = \frac{\sum_i (a_i * \%TBSA_i)}{\sum_i \%TBSA_i}$$

where $\%TBSA_i$ is the area of TW i (in % TBSA) and a_i denotes the % of wound area surgically excised for eschar removal of TW i.

10.3.5.6. *Incidence of reduction in interstitial/compartment pressure in circumferential extremities target wounds*

Interstitial/compartment pressure in circumferential extremities target wounds is measured within 1 hour (+30 min) prior to start of each eschar removal procedure and post-eschar removal. For each circumferential target wound and each eschar removal procedure a binary (yes/no) variable will be computed indicating whether reduction in interstitial/compartment pressure in that wound was present.

10.3.5.7. *POSAS*

The Patient Observer Scar Assessment Scale (POSAS) consists of two parts: a patient scale and an observer scale. Both scales contain six items that are scored numerically with 1-10. For each wound of a patient the total score of the patient scale will be computed as:

$$POSAS_P = \sum_{i=1}^6 p_i,$$

where p_i is the score the patient assigned to item i . The total score of the observer scale will be computed analogously as:

$$POSAS_O = \sum_{i=1}^6 o_i,$$

where o_i is the score the observer assigned to item i .

A total score for the POSAS is then obtained by summing the patient scale score and the observer scale score:

$$POSAS_{tot} = POSAS_P + POSAS_O.$$

For each patient the mean of $POSAS_{tot}$ over all TWs will be computed. Analogously the mean of $POSAS_{tot}$ over all donor site scars will be computed.

Additional to the quantitative scoring of the items they are also score qualitatively (for each item different categories are available). Absolute and relative frequencies of the categories for each item will be computed over all patients per treatment arm.

The POSAS will be computed for TWs and donor site scars at the long-term follow up visits.

10.3.5.8. *Incidence of surgical Escharotomy procedures on circumferential extremities target wounds*

For each circumferential extremities target wound a binary (yes/no) variable will be computed, indicating whether this wound was escharotomized. Furthermore, a binary (yes/no) variable for each patient will be computed indicating whether this patient had at least one circumferential extremities target wound which was escharotomized.

10.3.5.9. *Incidence of reduction in interstitial/compartment pressure in circumferential extremity wounds*

For circumferential extremity wounds the reduction in interstitial/compartment pressure will be computed as

$$Press_{diff} = Press_{base} - Press_{post}$$

where $Press_{base}$ is the interstitial/compartment pressure at baseline and $Press_{post}$ is the interstitial/compartment pressure after eschar removal. This will be done for each topical eschar removal procedure. Furthermore, for each circumferential extremity wound and each topical eschar removal procedure a binary (yes/no) variable will be computed indicating whether interstitial/compartment was reduced during the procedure.

10.3.5.10. *Incidence of surgically harvested donor sites wounds*

For each patient, the number of donor sites wounds will be calculated.

10.3.5.11. *% area of surgically harvested donor site wounds*

For each autograft procedure the % TBSA of the donor site is captured. These values will be summed up over all autograft procedures for each patient giving the % area of surgically harvested donor site wounds.

10.3.5.12. *Blood loss using changes in hematocrit following eschar removal procedures*

For each debridement procedure, the change in hematocrit will be calculated as the difference of the hematocrit value before the procedure and the hematocrit value 4 hours post the procedure. This difference in hematocrit values will be summed for each patient.

Furthermore, for each patient, the difference of the hematocrit value prior to the first debridement procedure and the hematocrit value 4 hours post the last debridement procedure will be calculated.

10.3.5.13. *Blood loss using changes in hemoglobin following eschar removal procedures*

For each debridement procedure, the change in hemoglobin will be calculated as the difference of the hemoglobin value before the procedure and the hemoglobin value 4 hours post the procedure. This difference in hemoglobin values will be summed for each patient.

Furthermore, for each patient, the difference of the hemoglobin value prior to the first debridement procedure and the hemoglobin value 4 hours post the last debridement procedure will be calculated.

10.3.5.14. *Blood loss comparing NexoBrid procedures to surgical procedures*

For a comparison of blood loss between NexoBrid procedures and surgical procedures, the blood loss per eschar removal procedure will be calculated as outlined in Section 10.3.3.3.1.

10.3.5.15. *Autograft related parameters*

The total number of grafting procedures per patient and per target wound will be computed. Procedure will be based on the date in the eCRFs per patient and per wound.

Furthermore, a binary (yes/no) variable will be computed indicating whether more than one autografting procedure was performed on a wound level as well as on a patient level.

The area of repeat autografting for each wound will be calculated as follows:

$$Area_{repeat} = \sum_{i=2}^n Area_i,$$

where n is the total number of autografting procedures for the specific wound and $Area_i$ is the area autograft in the i-th grafting procedure for that wound.

The area of repeat autografting on a patient level is calculated as the sum over the areas of repeat grafting over all TWs of that patient.

10.3.5.16. *Duration of hospitalization*

Duration of acute hospitalization will be computed as the difference in days between hospital admission and hospital discharge (initial hospitalization only).

10.3.5.17. *Time to reach 100% wound closure*

Information about date will be transformed to time in days from randomization. Time until 100% wound closure will be defined as the time (in days) until 100% wound closure has been achieved at a wound level. For wounds that do not reach 100% wound closure, the time will be censored at last date of wound closure assessment. In case one or more wounds do not reach complete wound closure, the time to wound closure at a patient level will be censored at the minimum of all wound wise censoring times.

10.3.6. **Laboratory values**

The following transformations will be applied to the central laboratory data obtained pre and post the eschar removal procedures:

Laboratory findings that are given in various units will be transformed to standard units. Laboratory values will be categorized as “abnormal (low)”, “normal” and “abnormal (high)” based on the reference limits of the labs.

Pre-post differences of laboratory values for each eschar removal procedure will be calculated.

Absolute and relative frequencies of “abnormal (low)”, “normal” and “abnormal (high)” findings will be calculated per laboratory value, eschar removal procedure and treatment arm.

10.4. **Multiple visits per time point**

Study visit time-points are scheduled at screening, pre eschar removal, eschar removal (treatment), post-treatment, hospital discharge, follow-up (weekly until wound closure, wound closure confirmation, three monthly visits post wound closure), long-term follow-up at 6, 12, 18

months and 24 months post wound closure confirmation and re-admission to hospital/day care (if done). One visit is expected for each time-point. The following approach is used if there are multiple visits per patient per time-point.

For all endpoints, if a subject has more than one visit with data at a time-point, the later non-missing evaluation will be used for analyses.

11. Statistical Analysis of Target Variables

The analysis is planned to be carried out in three stages, as described below.

1. The first analysis will be performed at the end of the Efficacy Assessment Period (EAP). This analysis will be the only inductive analysis of the trial and will include statistical tests for the primary and secondary endpoints as described below, as well for short-term safety endpoints (including time to wound closure). The analysis will be conducted, when 3 months had passed from the last patient reaching complete wound closure, in accordance with FDA guidance for industry *Chronic Cutaneous Ulcer and Burn Wounds — Developing Products for Treatment* “*Trial subjects generally should remain in the study for follow-up evaluation at least 3 months following complete wound closure. The purpose for this follow-up period is to help distinguish actual wound healing from transient wound coverage*”. At this time-point, data will be available for all patients on the primary end-point (proportion with complete eschar removal), the three secondary endpoints (proportion undergoing surgery, time to complete eschar removal, and blood loss) and short-term safety endpoints (including time to wound closure). Missing values for early drop outs etc. will be handled as described in Sections 10.1 and 10.2. The complete data set documented so far will be locked and analyzed as described above. In the analysis of adverse events and concomitant medication, for each patient only the data until the 3 months follow up will be analyzed in this stage. Data obtained after the 3 months follow up will be analyzed in the second and third stage of analysis. MVSS data, although captured in the eCRF for a few of the subjects at the stage of EAP, will not be included, revealed or analyzed during the EAP analyses.
2. The second analysis will be performed for the 12 months follow up period (STFU12) and will be started after the last patient has reached the 12m assessment. At this analysis, all accumulated safety data at the 12m follow-up will be analyzed, particularly the 12m MVSS assessment for cosmesis and function. The complete data set documented so far will be locked and analyzed as described below. In the analysis of adverse events for each patient only the data obtained after the 3 months follow up and until the 12 months follow up (including AEs and concomitant medications from the first stage that are ongoing) will be analyzed in this stage.
3. The third and final analysis covers the data of the long-term safety follow up (LTSFU24). It will be conducted after the last patient has reached the 24 months

assessment at last 12 months after (STFU12) analysis (stage 2). At this analysis, all accumulated safety endpoints at the 24m follow-up will be analyzed, particularly the 24m MVSS assessment for cosmesis and function. The complete data set documented during the trial will be locked and analyzed as described below (hard lock). In the analysis of adverse events for each patient only the data obtained after the 12 months follow up (including AEs and concomitant medications from the first or second stage that are still ongoing) will be analyzed in this stage.

Two “blinded assessors” are appointed in each clinical site during the site initiation visit. The assessor signs a “blinded assessor memo” which describes the procedures required to maintain the investigator blinded from the treatment arm. The first blinded assessor is responsible for the eschar removal assessment of the topical arms and is not involved with product application. All patients will complete the eschar removal treatment by the time of the first planned analyses of the acute stage and thus, there is no risk of unblinding of the first blinded assessor. The second blinded assessor is responsible for the wound closure and long-term assessments and is not involved with any eschar removal procedures. The second blinded assessor will remain blinded throughout the whole duration of the trial including after the acute and the first long-term (12 months) analysis results are available. To assure that patients’ treatment codes will not be revealed during the EAP analyses, all patients’ identification numbers will be Pseudonyms by data management before analysis is being performed and presented.

The data sets for analysis will be 100% SDVd and signed by the site investigator. Therefore, data changes are prevented during the further conduct of the study. Data management quality control actions will ensure that data used in the analysis is not changed afterwards see the Data Management Plan for further details.

For a better overview of this SAP, the statistical analysis of target variables described below will be displayed separately for these 3 stages of analyses.

All variables not mentioned explicitly in the following will be analyzed descriptively (as part of the case wise listing).

Unless otherwise specified, all statistical tests will be conducted against a two-sided alternative hypothesis, employing a significance level of 0.05.

11.1. First stage analysis – end of efficacy assessment period (EAP)

11.1.1. Demographics and Other Baseline Characteristics

For all considerations regarding the demographics and other baseline characteristics the full analysis set will be used.

The demographic and baseline information concerning

- Age
- Gender
- Ethnicity
- Race
- Height (cm)
- Weight (kg)
- BMI
- Physical examinations (categorized as normal, abnormal-NCS, abnormal-CS, not done):
 - Head, eyes, ears, nose and throat (HEENT)
 - Respiratory system
 - Cardiovascular system
 - Abdomen
 - Musculoskeletal / Extremities
 - Neurological
 - Lymph Nodes
- Vital signs:
 - Temperature
 - Heart rate
 - Respiratory rate
 - Systolic and diastolic blood pressure (mmHg)
 - Assessment of vital signs (normal, abnormal-NCS, abnormal-CS)
- Pain assessment:
 - VAS (mm)
 - Assessment of pain (normal, abnormal-NCS, abnormal-CS)
- Local laboratory:
 - Leukocyte count (WBC)

- Assessment of leukocyte count (normal, abnormal-NCS, abnormal-CS)
- Diabetes status (yes/no)
- HbA1c (%)
- Infections (yes/no for infections in last week before baseline)
- Relevant medical history (regarded as categorical variable)
- Burn history (on a patient level):
 - Time since injury
 - Etiology of injury (Fire/Flame, Scald, Contact)
 - Place of injury (Outdoors, Indoors, Car, Other)
 - Information whether patient was transferred from another facility
- General wound description (on a wound level):
 - Anatomical location (face, head, neck, etc.)
 - %TBSA of 2° SPT Burns
 - %TBSA of 2° DPT Burns
 - %TBSA of 3° FT Burns
 - Indicator (yes/no) of circumferential extremity involvement
 - Extremities at risk (not relevant, pain, paralysis, etc.)
 - Information whether escharotomy had been performed prior to randomization
 - Eschar description (white, moist, dry, etc.)
 - Information whether cleansing was performed
 - Information whether all superficial keratin (blister) were removed from wound
- Target wound description:
 - General wound description (see above; on a wound level; for target wounds only)
 - Information whether the wound was treated prior to enrollment (TWs)
 - Treatment of TWs prior to enrollment (SSD, Iodine, etc.)
- Target wound description (on a patient level):
 - Total wounds %TBSA
 - TWs DPT total area (%TBSA)
 - TWs FT total area (%TBSA)
 - Over TWs depth per patient (all full thickness, mixed, all deep partial thickness)
 - Overall TW area (SPT+DPT+FT)
 - %SPT area classified as <25% or ≥25% of TWs area
- Number of circumferential extremity wounds per patient

- Interstitial pressure (mmHg) for circumferential extremity wounds (on a wound level)
- Criteria for inclusion (met/not met)
- Counts of patients/wound per strata (%TBSA cut point 15%, depth cases 1-3, center)

will be analyzed descriptively with number of units, number of missing values, mean, standard deviation, min, max, median and quartiles in case of numeric values and counts and percentages in case of categorical items to describe the study population. The analysis will be done by treatment group and in total.

The descriptive results for all variables will be tabulated. Exemplary tables are presented in Section 13.2. Histograms will be produced for each continuous variable, bar plots for categorical variables. Figures can be seen in Section 13.3.

If any of the baseline factors, gender, age, percent SPT area (the area of SPT as a percentage of the total area of all TWs, classified as <25% or ≥25%), time from injury to randomization or number of TWs (1, 2, ≥3) are found to be significantly different between the treatment groups (Chi-squared tests (or in case of small estimated cell counts Fisher's exact test) for categorical variables and one-way analysis of variance for continuous variables) then the factor will be included as an extra adjusting covariate in the supportive analysis models for the primary and secondary efficacy endpoints and the comparative analyses of safety endpoints.

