If any of the baseline factors, gender, age, percent SPT area (the area of SPT as a percentage of the total area of all TWs, classified as <25% or ≥25%), time from injury to randomization or number of TWs (1, 2, ≥3) are found to be significantly different between the treatment groups, then, if possible, the factor will be included as an extra adjusting covariate in a supportive analysis of the primary endpoint.

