11.1.3. Secondary Efficacy variables

The secondary endpoints will be analyzed as described below and will compare efficacy in the NexoBrid group with the SOC group. Missing data will be handled by the methods described in Section 10.1. All secondary endpoints will be analyzed using the FAS. Sensitivity analyses will include analyzing the endpoints using the PP as analysis population.

11.1.3.1. *Incidence of surgical excision*

This is a binary yes/no variable and the proportion of patients who need excision for eschar removal will be compared using logistic regression. The explanatory variables in the model will include treatment, and the following variables: overall TW depth (all TWs full thickness, mixed TWs, all TWs deep partial thickness), “Total %TBSA per patient” and number of TWs (1, 2, ≥3). The odds ratio of requiring surgery for NexoBrid versus SOC will be estimated from the model, as well as 95% confidence intervals and the level of statistical significance. The results

will be displayed as shown in Table 6 and Table 7. Bar plots will be shown for the proportions of patients who needed excision for eschar removal.

If numerically possible, as a supportive analysis, the variable treatment center will be added into the logistic regression model and the analysis repeated.

As a sensitivity analysis, the logistic regression outlined above will be repeated using the PP as analysis population.

If any of the baseline factors, gender, age, percent SPT area (the area of SPT as a percentage of the total area of all TWs, classified as <25% or ≥25%), time from injury to randomization or number of TWs (1, 2, ≥3) are found to be significantly different between the treatment groups, then the factor will be included as an extra adjusting covariate in the logistic regression model described above as additional analysis.

As supportive analysis, the incidence of surgical excision for eschar removal will be compared between NexoBrid and Gel Vehicle using the same explanatory variables as in the main analysis of this endpoint.

A further supportive analysis will repeat the analysis (NexoBrid versus SOC) as described above, but on a wound level. I.e. a mixed logistic regression model with explanatory variables treatment, TW depth, %TBSA per wound and number of TWs and a random effect for patient will be performed.

11.1.3.2. *Time to complete eschar removal*

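### Extra covariates enter the supportive models only if a 5% baseline test is significant, so chance imbalance rather than prognostic value decides the adjustment

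*SAP*

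**What the plan says.** Section 11.1.1 sets the rule. Its list opens with "If any of the baseline factors, gender, age, percent SPT area" (in two classes) and goes on to the interval between injury and randomization and the count of target wounds (one, two, three or more). The consequence of a significant baseline test is stated as follows: "then the factor will be included as an extra adjusting covariate in the supportive analysis models". Categorical factors are tested by chi-squared or Fisher's exact test, continuous ones by one-way analysis of variance. No separate level is given for these tests, so the default at the start of Section 11 applies, namely two-sided testing "employing a significance level of 0.05".

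The rule recurs endpoint by endpoint:

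- **Primary (11.1.2):** five factors; if possible, "the factor will be included as an extra adjusting covariate in a supportive analysis of the primary endpoint".
- **Surgical excision (11.1.3.1):** five factors; "then the factor will be included as an extra adjusting covariate in the logistic regression model described above as additional analysis".
- **Time to complete eschar removal (11.1.3.2):** five factors. Under proportional hazards, each imbalanced factor and its interaction with treatment go into a separate Cox model.
- **Blood loss (11.1.3.3):** four factors, without number of target wounds.
- **Time to wound closure (11.1.4.1):** three factors: gender, age and percent SPT class.

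Other covariates are fixed without any baseline test. For excision, "The explanatory variables in the model will include treatment, and the following variables: overall TW depth", Total %TBSA and number of target wounds. The main Cox model for eschar removal has these plus center group. The supportive blood loss model has these plus center group and number of debridement procedures. For the primary endpoint, depth, %TBSA and center group each enter a supportive exact logistic model where this can be estimated.

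**The concern.** In a randomized trial a significant baseline difference is a chance event. Its p-value reflects the size of the imbalance and the sample size, and says nothing about whether the factor predicts outcome. A covariate is worth adjusting for because it predicts outcome, and that can be judged before any data are seen. Under this rule a prognostic factor with a moderate, non-significant imbalance is left out, while a factor unrelated to outcome that happens to be imbalanced is put in. The content of the supportive models is then unknown until the data arrive. They do least in the situation they are meant for, which is checking that the main result does not rest on an imbalance in other baseline factors.

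**Working it through.** **Inputs from the SAP.** Level 0.05 two-sided (Section 11, opening). Factors screened: 5, or 4 or 3 by endpoint (11.1.1 to 11.1.4.1). Planned arms 75 NexoBrid, 75 SOC, 25 Gel Vehicle (9.3.1). Anticipated Gel response 0 to 0.10 (9.1.1).

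**The plan's own figures.** The rule carries no figure except the 0.05 level. The sample-size figures reproduce and do not depend on the rule. Fisher power is 0.908 for 65 vs 13 and 0.904 for 43 vs 43 (stated 90%). Events are 4 × (1.96 + 1.28)² / 1.23² = 27.75, so 28 as stated.

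**Step 1: how often a factor enters.** With valid randomization each test rejects with probability about 0.05. With k independent tests, P(no factor added) = 0.95^k.

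| Endpoint | k | None added | At least one added |
|---|---|---|---|
| Primary | 5 | 0.95⁵ = 77.4% | 22.6% |
| Secondary endpoints | 4 | 0.95⁴ = 81.5% | 18.5% |
| Time to wound closure | 3 | 0.95³ = 85.7% | 14.3% |

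For the secondary endpoints k is 4 because number of target wounds is already in the excision model, the Cox model and the supportive blood loss model. Listing it again as an extra factor in 11.1.3.1 and 11.1.3.2 has no effect as adjustment.

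**Step 2: imbalance that passes unadjusted.** For a continuous factor, the observed difference needed for significance is about 1.96 × √(1/n₁ + 1/n₂). This is 1.96 × √(1/75 + 1/75) = 0.32 SD for NexoBrid vs SOC, and 1.96 × √(1/75 + 1/25) = 0.45 SD for NexoBrid vs Gel. For a factor with an assumed correlation of 0.5 with a continuous outcome, an imbalance just under 0.32 SD shifts the unadjusted difference by up to 0.5 × 0.32 = 0.16 SD, and the rule leaves it uncorrected.

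**Step 3: precision.** Simulation of 8,000 trials: arms 75/75/25, baseline screen by three-arm analysis of variance at 0.05, then a 75 vs 75 linear model. The true effect of 0.46 SD and the covariate–outcome correlations r are assumptions, since the SAP gives neither.

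| r | Unadjusted power | SAP rule | Always adjusted |
|---|---|---|---|
| 0 | 0.80 | 0.80 | 0.80 |
| 0.3 | 0.80 | 0.80 | 0.83 |
| 0.5 | 0.81 | 0.81 | 0.90 |
| 0.7 | 0.80 | 0.82 | 0.97 |

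The factor entered in 4.6% to 4.9% of trials, with no relation to r. Type I error at r = 0.7 was 0.041 under the rule and 0.050 with fixed adjustment. The model is continuous, so it is closest to blood loss and only indicative for the odds ratio and hazard ratio analyses.

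**Step 4: consistency.** The text of 11.1.3.2 adjusts for imbalanced factors only. Its code for non-proportional hazards puts gender, age group and percent SPT group into STRATA together and omits time from injury. That allows 3 × 3 × 2 × 5 × 2 × 2 × 2 = 720 strata for 150 patients, against 3 × 3 × 2 × 5 = 90 in the main code.

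**The case against.** The strongest reply is that little depends on the rule. It is written down in advance and leaves the analyst no discretion. The primary test is an unadjusted Fisher's exact test, and no main efficacy analysis uses the screened result. The simulation shows no inflation of type I error. All of this stands.

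Some of the factors are also partly covered elsewhere. Percent SPT class has its own subgroup analyses (11.1.11.2 and 11.1.11.3), and SPT area is in the accelerated failure time code for wound closure. Time to eschar removal is repeated from the date of injury, and the 84-hour consent limit narrows the spread of time from injury. This reduces the loss. It does not turn the baseline test into a sound entry rule.

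Three stronger readings are tempting, and the SAP does not support them:

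- **That strong prognostic factors are usually left out.** Section 7.1 expects outcomes to correlate with total burn area and depth, and both are adjusted for without a baseline test. The SAP nowhere calls gender, age, percent SPT class or time from injury strong predictors.
- **That in 77% of trials nothing is adjusted for.** The 77% means that no extra factor joins those already fixed, and it applies to the primary endpoint only.
- **That the screen runs across all three arms.** One-way analysis of variance and the plain reference to treatment groups suggest it, but the method also serves two groups. The wording is ambiguous.

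Forcing a full covariate set into the primary model would also fail. With 25 × 0 to 25 × 0.10 = 0 to 2.5 Gel responders expected, a joint model will often not be estimable.

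**Conclusion.** The point holds as a limited weakness of the supportive analyses. A 5% baseline test decides whether the screened factors enter, so each enters about 5% of the time regardless of prognostic value. No extra factor is added in about 77% (primary), 81% (secondary) or 86% (wound closure) of trials. These percentages assume valid randomization and independent tests; correlated factors would change them somewhat. The supportive analyses then add little precision or protection beyond the covariates already fixed. How much is lost depends on correlations that the SAP does not give: in the simulation nothing at r = 0, and 0.09 to 0.15 in power at r = 0.5 to 0.7. The main efficacy tests, alpha and sample size are unaffected. This is a desirable improvement and not a threat to the trial's conclusions.

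**What to change.** Drop the baseline significance tests as the entry rule; descriptive baseline tables can stay.

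- **Secondary endpoints and time to wound closure:** fix one supportive covariate set now, on top of the covariates already listed. An example is age, percent SPT class (<25% / ≥25%) and time from injury to randomization. Include it whatever the baseline p-values.
- **Consistency:** use the same list in Sections 11.1.1 to 11.1.4.1 and in the STRATA code of 11.1.3.2. There time from injury needs a category cut fixed in advance, and the list should stay short because of the number of strata.
- **Primary endpoint:** add percent SPT class and number of target wounds one at a time in supportive exact logistic models, if estimable, as 11.1.2 already does for depth, %TBSA and center group.

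The cost is SAP wording and a few degrees of freedom in supportive models. All the covariates are already planned for collection.
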